#### **6.2.3. Supportive Primary Efficacy Endpoint Analysis**

The supportive primary efficacy endpoint is the change from baseline to week 4 in LP SUVmean (Avg SUVmean).

The same statistical methods used for the analysis of the primary efficacy endpoints of Part 2 above will be used to summarize the supportive primary efficacy endpoints (Summaries 15.2.2.1 to 15.2.2.8).

#### **6.2.4. Sub-Group Analyses**

No subgroup analysis will be performed for this study.

### **6.3. Secondary Efficacy Endpoints and Analysis.**

The secondary efficacy endpoints will be descriptively summarized using the same statistical methods used for the primary efficacy endpoint of Part 2 above. In addition, to demonstrate the relationship between the benefit observed on imaging (PET/CT scan) with the secondary endpoints, the correlation between the change from baseline to week 4 for each secondary endpoint and change from baseline to week 4 in GLG ( $\Delta$ GLG) will be calculated using Spearman's Rho.

No inferential statistics will be used for the secondary endpoints analyses.

#### **6.3.1. Blood Eosinophil Count**

##### **6.3.1.1. Definition**

The first secondary efficacy endpoint is change from baseline (Day 1/Visit 4) to weeks 2, 4, and 6 in blood eosinophil count.

##### **6.3.1.2. Analysis**

Blood eosinophil count value and change from baseline to each of the post-baseline visits (2, 4, and 6 weeks, after randomization) will be descriptively summarized, by treatment group, based on the ITT and FAS. The difference in mean changes from baseline between reslizumab and placebo, and Spearman's Rho will also be summarized and reported (Summaries 15.2.3.1 and 15.2.3.2).

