## 2.2. Randomization and Blinding

This is a randomized, double-blinded, placebo-controlled, parallel-group study. After the 2 baseline PET/CT scans and successful completion of all requirements (Part 1), patients will be randomly assigned 1:1 in a double-blind fashion to receive either placebo or iv 3.0 mg/kg reslizumab. In order to maintain the blind, each patient will be assigned a unique identifier number and all reference to the patient will be by using this identifier.

Patients will be randomly assigned to treatment groups by means of a computer-generated randomization list. The specifications for randomization will be under the responsibility and oversight of Teva Global Statistics. The output of the randomization process will be a patient randomization list.

The sponsor's clinical personnel involved in the study will be blinded to the study drug identity until the database is locked for analysis and the treatment assignment is revealed, with the exception of the bioanalytical group who will not be blinded to facilitate ADA sample analysis and an un-blinded person who will be responsible for randomization assignment. Additionally, in order to maintain the study blind, blood and sputum eosinophil levels assessed after study drug administration will not be available to investigators, their blinded staff, the sponsor, and blinded members of the clinical research organization. There will be un-blinded data management, un-blinded site staff, and an un-blinded CRA who will not sit on the study team and be responsible for un-blinded eosinophil data.

In case of a serious adverse event, pregnancy, or in cases when knowledge of the study drug assignment is needed to make treatment decisions, the investigator may unblind the patient's drug assignment as deemed necessary, mainly in emergency situations. When a blind is broken, the patient will be withdrawn from the study and the event will be recorded on the case report form (CRF). The circumstances leading to the breaking of the code should be fully documented in the investigator's study files and in the patient's source documentation. Treatment assignment should not be recorded in any study documents or source document.

At the time of analysis (after the end of study), after receiving unblinding request from Teva statistician, the service provider will provide the unblinded treatment assignment according to the processes defined in the relevant Standard Operating Procedure (SOP).

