## 2.4. Sample Size and Power Considerations

This study is exploratory in nature; therefore, no formal hypothesis testing is planned. Based on clinical and practical considerations, 5 healthy subjects and 10 eosinophilic asthma patients (5 patients treated with reslizumab, and 5 patients treated with placebo) is considered adequate for:

1. a validation of the ability of PET/CT to differentiate patients with eosinophilic asthma from HC subjects,
2. an evaluation of the effect of reslizumab versus placebo on inflammation of the lungs.

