Relative differences between the first (V2) and second (V3) measurements will be summarized, by total/regional lung and patients/HC group, using descriptive summary statistics, based on enrolled analysis set (Summary 15.2.1.1).

Variability between HC group and individual patients with eosinophilic asthma (Part 1):

The planned method to assess whether the difference in GLG measure between HC subjects, as a group, and individual patients (one-by-one) with eosinophilic asthma is  $\geq 5\%$  will be calculated as follows:

- For Females: Relative difference of GLG =  $(GLG6i-GLG5f)/GLG5f$ , i.e., difference in GLG (based on average of 2 measurements) between each individual patient with asthma and the mean of HC group, for females.
- For Males: Relative difference of GLG =  $(GLG6i-GLG5m)/GLG5m$ , i.e., difference in GLG (based on average of 2 measurements) between each individual patient with asthma and the mean of HC group, for males.

5=average of 2 GLG measurements (1 and 2) of all HCs by sex

6=average 2 GLG measurements (3 and 4) for each individual asthma patients

GLG6i will be calculated for each individual male/female patient using his/her two GLG measurements at V2 and V3 (Part 1). If this amount is  $\geq 5\%$  then the patient will be randomized.

Relative differences in GLG measures between the HC group and individual patients with asthma will be summarized for each sex, by total lung/regional lung, using descriptive summary statistics, based on enrolled analysis set (Summaries 15.2.1.2 and 15.2.1.3).

Relative change from baseline to week X in GLG ( $\Delta$ GLG) (Part 2):

$\Delta$ GLG =  $(GLGwX - GLG_{baseline})/GLG_{baseline}$

wX= post-randomization week (week 2 /V5, week 4/V6, and week 6/V7).

GLG Baseline= the average of two measurements at Visits 2 and 3 of Part 1 (see section 4.2 of the SAP).

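### The arm difference in blood eosinophils is planned only as an unadjusted difference in change from Visit 4; a descriptive Visit 4-adjusted difference would be a cheap gain in precision if depletion is strong

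*SAP*

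**What the plan says.** SAP 6.3.1.1 sets the endpoint: "The first secondary efficacy endpoint is change from baseline (Day 1/Visit 4) to weeks 2, 4, and 6 in blood eosinophil count". SAP 6.3.1.2 then summarises "Blood eosinophil count value and change from baseline to each of the post-baseline visits" by treatment group and adds "The difference in mean changes from baseline between reslizumab and placebo", together with Spearman's rho against GLG change. The method is carried over from the imaging endpoint: "The secondary efficacy endpoints will be descriptively summarized using the same statistical methods used for the primary efficacy endpoint of Part 2 above". Protocol 9.5.4.3 says the same, so the two documents agree.

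For GLG, SAP 6.2.1 uses a relative scale: "Relative change from baseline to week X in GLG". No such scaling is stated for eosinophils.

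The planned size is "5 patients treated with reslizumab, and 5 patients treated with placebo" (SAP 2.4). SAP 2.2 says that "patients will be randomly assigned 1:1 in a double-blind fashion" and describes no stratification by eosinophil count. Neither document plans a model with a baseline covariate. The SAP states that "no formal hypothesis testing is planned", and SAP 6.3 excludes inferential statistics for the secondary endpoints.

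On the drug effect, Protocol 1.3.2.2 treats a fall in blood eosinophils as expected pharmacology and gives no size. SAP 2.2 withholds post-dose counts to protect the blind, which suggests an effect large enough to reveal treatment.

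**The concern.** Subtracting baseline with a coefficient of 1 works well when follow-up tracks baseline closely in both arms. A depleting drug breaks this in the treated arm. If counts fall to a small fraction of V4 whatever the starting level, the follow-up count hardly depends on V4, and the change is nearly minus V4. The arm that happens to start higher then shows a larger fall for that reason alone.

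With 5 per arm and no stratification, a sizeable chance imbalance is likely. The plan reports one number for the arm contrast, with no interval, so a reader cannot see how much of it reflects starting levels. The V4 count needed to reduce this is already collected.

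A related point concerns the planned correlation. Within treated patients, ranking by raw change is then mostly ranking by V4 count, whereas GLG change is expressed relative to its own baseline.

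**Working it through.** The documents give no variance, effect size or power for this endpoint, so there is no planned figure to reproduce.

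**Inputs from the documents.** 5 per arm (SAP 2.4); 1:1 allocation with no stratification described (SAP 2.2); contrast of mean changes from V4 (SAP 6.3.1.2).

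**Assumed inputs.** Mean V4 count 600 cells/µL; coefficient of variation (CV) 25-60%; correlation ρ between V4 and week 4 on placebo 0.5-0.85; depletion 50-95%.

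**Step 1: size of the chance imbalance.** Let s be the SD of V4 counts and D the arm difference in mean V4 count. SD(D) = s√(2/5). For s = 300 this is about 190 cells/µL; for s = 240 (CV 40%), about 152.

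**Step 2: how far imbalance moves the raw difference.** Let the placebo SD be the same at both times. Let treated post-dose counts have SD qs and correlation r with V4. Put b = (ρ + qr)/2. The expected shift per unit of D is b − 1. With complete depletion (q = 0) and ρ = 0.7, b = 0.35 and the shift is −0.65.

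**Step 3: variances, in units of s²/n.**
- Change score: (1 + q² − 2qr) + 2(1 − ρ). At q = 0 this is 3 − 2ρ.
- Adjusted for V4 with a common slope: [(q² − 2bqr + b²) + (1 − 2bρ + b²)] × 7/6. At q = 0 this is (1 − ρ²/2) × 7/6. The 7/6 is the cost of estimating the slope with 8 within-arm degrees of freedom: 1 + 1/(8 − 2).

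| ρ (q = 0) | Change score | Adjusted | Variance removed |
|---|---|---|---|
| 0.5 | 2.00 | 0.875 × 7/6 = 1.021 | 49% |
| 0.7 | 1.60 | 0.755 × 7/6 = 0.881 | 45% |
| 0.9 | 1.20 | 0.595 × 7/6 = 0.694 | 42% |

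**Step 4: simulation at 5 per arm with incomplete depletion.** Mean 600, SD 300, ρ from 0.3 to 0.9, normal and lognormal counts:

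| Depletion | Variance removed by V4 adjustment |
|---|---|
| 95% | 41-55% |
| 90% | 40-54% |
| 80% | 37-50% |
| 60% | 27-43% |

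A second simulation used lognormal counts, CV 25-60%, ρ 0.5-0.85, and a residual fraction that varies between treated patients (CV 50%). Adjustment removed about 33-52% at 80-95% depletion and about 3-38% at 50-60%. At CV 40%, ρ = 0.7 and 95% depletion, the standard error fell from 131 to 96 cells/µL; 1 − (96/131)² = 46%. At 80-95% depletion, each 1 cell/µL of V4 imbalance moved the raw difference by about 0.5-0.7 and the adjusted difference by about 0.

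**Step 5: what one SD of imbalance does.** At 90% depletion, ρ = 0.7 and s = 300, the simulated shift is 0.62 per unit of D. One SD of imbalance moves the difference by 0.62 × 190 ≈ 118 cells/µL, against a mean effect of about −540, or 118/540 = 22%.

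**Step 6: ranks in the treated arm.** At 80-95% depletion in the second simulation, raw change had a mean rank correlation of −0.80 to −0.99 with V4 count, and only 0.03 to 0.34 with the count relative to V4. This largely follows from generating the treated count as V4 times a fraction.

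**Alternative remedy.** Comparing post-dose means without a model is not a safe substitute. At 60% depletion and ρ = 0.9 its variance was 17-19% higher than that of the change score.

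**The case against.** The strongest reply is that nothing in the plan is wrong. The study is exploratory, no standard error, interval or test is planned for this contrast, and the raw difference is unbiased over randomisation. V4 is used, since it is subtracted for every patient. Counts as well as changes are tabulated by arm (SAP 6.3.1.2, and hematology again in SAP 8.4), so an imbalance could be noticed. In the example, one SD of imbalance shifts the estimate by about a fifth, which would not hide a large fall in counts. All of this stands. It limits the point to precision and to error given the imbalance that actually occurs; tabulating counts shows an imbalance but does not correct the reported contrast.

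The adjusted model also has a cost. Strong depletion implies different slopes in the two arms, so a common slope is an approximation. With skewed counts it brought the estimate up to about 6% closer to zero.

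The criticism of the correlation is weaker. SAP 1.1.2 aims to correlate imaging benefit with reductions in eosinophil counts, and absolute reduction is a fair reading of that. SAP 6.3 does not say whether rho is pooled or by arm; if pooled, the separation between arms also contributes. Nothing here shows that the relative scale ranks response better.

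**Conclusion.** This is a cheap improvement rather than an error. Under assumed strong depletion (80-95%), with CV 25-60% and placebo correlation 0.5-0.85, a V4-adjusted difference has about 33-52% less variance than the planned one and is almost insensitive to V4 imbalance. At 50-60% depletion the gain is about 3-38%.

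A reader might infer more than the documents support:
- That the plan disregards V4 or gives a biased estimate. It subtracts V4, and randomisation protects the mean.
- That a gain of a third to a half is established. It depends on a depletion size, spread and correlation that neither document states.
- That the planned rho is invalid. A rho on the relative scale is a reasonable sensitivity analysis, not a correction.
- That FeNO and AQLQ would gain likewise. The mechanism is cell depletion, and no such argument or correlation is available for them. With equal slopes in both arms the variances are 2(1 − r) for change and (1 − r²) × 7/6 adjusted: at r = 0.7, 0.60 against 0.595; at r = 0.9, 0.20 against 0.222, a slight loss.

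**What to change.** Keep all planned summaries. In SAP 6.3.1.2 add, labelled as descriptive, the week-4 arm difference in blood eosinophils from a linear model with treatment and V4 count, and show V4 counts by arm beside it. As a sensitivity analysis, also compute the eosinophil-GLG Spearman rho with eosinophil change taken relative to V4, the kind of scale SAP 6.2.1 already uses for GLG.

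The cost is a few lines of SAP text and one further column, from data already collected. The statistical price is one degree of freedom out of 10 patients and the common-slope approximation, which is why the adjusted figure should stand beside the raw difference and not replace it. No change is needed for FeNO or AQLQ on this ground.

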#### **6.3.2. Forced Expiratory Volume (FEV1)**

##### **6.3.2.1. Definition**

FEV1 will be measured using spirometry. The FEV1 is the volume of air which can be forcibly exhaled from the lungs in the first second, measured in liters.

The second secondary efficacy endpoint is the change from baseline (Day 1/Visit 4) to weeks 2, 4, and 6 in FEV1.

##### **6.3.2.2. Analysis**

FEV1 value and change from baseline to each of the post-baseline visits (2, 4, and 6 weeks, after randomization) will be descriptively summarized, by treatment group, based on the ITT and FAS. The difference in mean changes from baseline between reslizumab and placebo, and Spearman's Rho will also be summarized and reported (Summaries 15.2.3.3 and 15.2.3.4).

### **6.3.3. Fractional Exhaled Nitric Oxide (FeNO) Measurements**

#### **6.3.3.1. Definition**

The third secondary efficacy endpoint is change from baseline to weeks 2, 4, and 6 in FeNO measurements.

#### **6.3.3.2. Analysis**

FeNO measurements and change from baseline to each of the post-baseline visits (2, 4, and 6 weeks, after randomization) will be descriptively summarized, by treatment group, based on the ITT and FAS. The difference in mean changes from baseline between reslizumab and placebo, and Spearman's Rho will also be summarized and reported (Summaries 15.2.3.5 and 15.2.3.6).

### **6.3.4. AQLQ score**

#### **6.3.4.1. Definition**

The fourth secondary efficacy endpoint is change from baseline (Day 1/Visit 4) to weeks 2, 4 and 6 in AQLQ.

The AQLQ+12 is a modified version of the standardized self-administered AQLQ questionnaire, which was developed to measure functional impairments experienced by adults  $\geq 17$  years of age. The AQLQ+12 is valid for patients aged 12 to 70 years and includes 32 questions/items in 4 domains: asthma symptoms (12 questions: 6, 8, 10, 12, 14, 16, 18, 20, 22, 24, 29, 30), activity limitation by asthma (11 questions: 1 to 5, 11, 19, 25, 28, 31, 32), emotional function (5 questions: 7, 13, 15, 21, 27) and exposure to environmental stimuli (4 questions: 9, 17, 23, 26). Patients are asked to recall their experiences during the previous 2 weeks and score their response options to each of the questions on a 7-point scale where 7 = no impairment and 1 = severe impairment.

The questionnaire is analyzed directly from the scores recorded. First, the overall AQLQ score is calculated as the mean of all 32 responses for each patient and the individual domain scores are the means of the responses within each domain for each patient. For details of the AQLQ+12 questionnaire, see Appendix B of the protocol and Juniper et al (1992).

AQLQ scores were recorded at Visits 4 (Baseline, Day 1), 5, 6 and 7 of Part 2 (see Table 1).

#### **6.3.4.2. Analysis**

Mean AQLQ scores and change from baseline to each of the post-baseline visits (2, 4 and 6 weeks after randomization) will be descriptively summarized, for overall score, and each domain, and treatment group, based on the ITT and FAS. The difference in mean changes from baseline between reslizumab and placebo, and Spearman's Rho will also be summarized and reported (Summaries 15.2.3.7 and 15.2.3.8).

## **6.4. Exploratory Efficacy Endpoints Analysis**

No inferential statistics will be used for exploratory efficacy endpoints and analyses.

#### **6.4.1. Biological Markers of Inflammation and Asthma: IgE, DPP4, 25-hydroxy vitamin D, eotaxin-1, -2, and -3, TARC, MCP-1 and MCP-4, ILC2**

##### **6.4.1.1. Definition**

Blood samples for assessment of biological markers of inflammation and asthma will be collected at Visits 4, 5, 6, and 7 and processed using the procedures in place at the investigational center [REDACTED]

##### **6.4.1.2. Analysis**

Change from baseline (Day 1/Visit 4) to each of the post-baseline visits (2, 4, and 6 weeks after randomization) in biological markers of inflammation and asthma, will be summarized using descriptive statistics (n, mean, standard deviation, median, minimum, and maximum) by treatment group, based on FAS. The difference in mean changes from baseline between reslizumab and placebo will also be summarized and reported for each biological marker (Summary 15.2.4.1).

In addition, to explore the relationship between the benefit observed on imaging (PET/CT scan) with the exploratory biomarker endpoints, the correlation between the change from baseline to week 4 for each biomarker endpoint and change from baseline to week 4 in GLG ( $\Delta$ GLG) will be calculated using Spearman's Rho.

#### **6.4.2. Biological Lung Function Variables: FVC, PEFR, FEF25%-75%**

##### **6.4.2.1. Definition**

Forced vital capacity (FVC), PEPR, and FEF25%-75% will be measured at baseline (Visit 4) and post-baseline visits 5, 6 and 7, using spirometry (see section 6.2 of the protocol).

The FVC is the volume of air that can be forcibly blown out after full inspiration, measured in liters. The FEF25%-75% is the forced expiratory flow at 25% to 75% forced vital capacity. The PEFR is the peak expiratory flow rate, measured in L/min.

Spirometry will be conducted according to American Thoracic Society/European Respiratory Society 2005 procedural guidelines. The National Health and Nutrition Survey III reference equations will be used.

##### **6.4.2.2. Analysis**

FVC, PEPR, and FEF25%-75% values and change from baseline to each of the post-baseline visits (2, 4, and 6 weeks after randomization) will be summarized using descriptive statistics (n, mean, standard deviation, median, minimum, and maximum), by treatment group based on FAS. The difference in mean changes from baseline between reslizumab and placebo will also be summarized and reported for each lung function variable (Summary 15.2.4.2).

In addition, correlation between change from baseline to week 4 in FVC, PEPR, and FEF25%-75% and change from baseline to week 4 in GLG ( $\Delta$ GLG) will be calculated using Spearman's Rho correlation.

### **6.4.3. Upper-body Uptake of FDG in Lymph Nodes and Bone Marrow**

#### **6.4.3.1. Definition**

The uptake of FDG in the lymph nodes and bone marrow of the upper body (lower limit of iliac crest) as measured by the PET/CT imaging parameters indicated for the primary efficacy variable (see section 6.1.2 of the protocol and section 6.2.1 of the SAP).

#### **6.4.3.2. Analysis**

Change in values of uptake of FDG in the lymph nodes and bone marrow of the upper body from baseline (the average of 2 measurements at V2 and V3 of Part 1) to each of the post-baseline visits (weeks 2, 4, and 6 after randomization) will be summarized using descriptive statistics (n, mean, standard deviation, median, minimum, and maximum), by treatment group based on FAS. The difference in mean changes from baseline between reslizumab and placebo will also be summarized and reported for total lymph node inflammation and total bone marrow inflammation (Summary 15.2.4.3).

### **6.4.4. Sputum Eosinophils**

#### **6.4.4.1. Definition**

For those patients who can produce sputum, sputum sampling for eosinophils will be performed at Visits 4, 5, 6, and 7.

#### **6.4.4.2. Analysis**

Change in values of sputum eosinophils from baseline (Day 1/Visit 4) to each of the post-baseline visits (weeks 2, 4, and 6 after randomization) will be summarized using descriptive statistics (n, mean, standard deviation, median, minimum, and maximum), by treatment group based on FAS. The difference in mean changes from baseline between reslizumab and placebo will also be summarized and reported (Summary 15.2.4.4).

In addition, correlation between change from baseline to week 4 in sputum eosinophils and change from baseline to week 4 in GLG ( $\Delta$ GLG) will be calculated using Spearman's Rho correlation.

## **7. MULTIPLE COMPARISONS AND MULTIPLICITY**

No adjustments will be made for the preplanned multiple comparisons/endpoints.

## **8. SAFETY ANALYSIS**

### **8.1. General**

The safety analyses for Part 2 of the study will be presented by treatment group and overall, based on the safety analysis set.

In addition, safety analysis for Part 1, based on the enrolled analysis set, will be presented by study participants status (HCs vs patients with asthma) and overall.

Combined safety analysis presenting safety data for Part 1 and Part 2 of the study may be provided, as deemed necessary.

Individual listings will also be provided.

### **8.2. Adverse Events**

All adverse events will be coded using the latest available version of the Medical Dictionary for Regulatory Activities (MedDRA), associated with five levels of classifications: a System Organ Class (SOC), a High Level Group Term (HLGT), a High Level Term (HLT), a Preferred Term (PT) and a lowest Level Term (LLT).

Only Treatment Emergent Adverse Event (TEAE), defined as events occurring after the first drug administration and until the end of the study, will be presented, based on Safety analysis set.

Similarly, AEs occurring between ICF signing and end of Part 1 will be presented based on Enrolled analysis set.

In the AE summary tables each patient will be counted only once in each preferred term or system organ class category for the analyses of safety. Summaries will be presented for all adverse events by treatment group, and overall as following:

- All AEs sorted by SOC and PT based on Safety analysis set (Summary 15.3.1.1) and on Enrolled analysis set (Summary 15.3.1.2)
- All AEs sorted by PT based on Safety analysis set (Summary 15.3.1.3) and on Enrolled analysis set (Summary 15.3.1.4)
- Treatment-related AE sorted by SOC and PT based on Safety analysis set (Summary 15.3.1.5)
- Serious AE sorted by SOC and PT based on Safety analysis set (Summary 15.3.1.6)
- Non serious AE sorted by SOC and PT based on Safety analysis set (Summary 15.3.1.7)
- AE sorted by SOC, PT and severity based on Safety analysis set (Summary 15.3.1.8).

Asthma deterioration will be descriptively summarized for safety analysis set (Summary 15.3.1.9).

Patient listings of serious adverse events and adverse events leading to withdrawal will be presented. Suspected anaphylaxis/hypersensitivity and CPK reactions will be listed individually (Listings 16.2.8.12 and 16.2.8.13).

